7.2. Discussion of Design and Control

7.2.1. Introduction

The present study is a prospective, Phase 3, randomized, multicenter, 2-arm, active-control, open-label, parallel, 24-week treatment study in patients with T1DM on basal-bolus insulin

therapy, followed by a 4-week post-treatment follow-up. The trial is designed to allow a head-to-head comparison of the efficacy and safety of 2 basal insulin analogs with the same primary amino acid sequence (LY2963016 and Lantus®) in patients with T1DM. The study design includes screening, randomization, treatment (24 weeks until primary endpoint assessment) and post-treatment follow-up periods. The Treatment Period is composed of a Titration Period and a Maintenance Period. It is expected that most of the basal and bolus insulin dose adjustments should occur during the initial titration period (Week 0 through Week 6); however, titration could extend up to Week 12 for patients who need more intensification to achieve glycemic targets. It is expected that insulin dose adjustments during the Maintenance Period would be for safety such as hypoglycemia or unacceptable hyperglycemia.

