7.2.2.4. Study Visits (Visit 3 to Visit 13 or Early Discontinuation)

Patients will come to the investigator site at 2-week intervals between Visit 2 and Visit 8. From Visit 8 to Visit 13, patients will come to the clinic at 6-week intervals. Visit 801 is a 4-week follow-up clinic visit ([Attachment 1](#)).

Between Visit 2 and Visit 4 and Visit 4 and Visit 6, Visit 6 and Visit 8, Visit 8 and Visit 11, there are telephone visits (Visits 3, 5, 7, 9 and Visit 10), which are described separately (Section 7.2.2.3).

The following activities will occur during Visits 3 to Visit 13 or Early Discontinuation (ED):

- study diaries collected and reviewed for BG levels, episodes of hypoglycemia, injection-site skin reactions, and insulin self-administration (Section [7.2.2.2.1.1](#))
- distribute study diaries (not completed at ED)
- dispense glucose-meter supplies as needed (not completed at ED)
- dispense study drug/device at Visits 8, 11, and 12 (not completed at Visit 13 or at ED)
- collection of blood sample for HbA1c assessment to determine efficacy of treatment values for each patient at Visits 8, 11, 12, and Visit 13 (or ED)
- transfer data from study diaries into eCRF (including previous day's insulin dose from last telephone visit)
- collect study drug at Visits 8, 11, 12, and Visit 13 (or ED)
- the previous day's insulin dose
- titration of insulin/adjust insulin dose as needed during visits (See [Attachment 5](#); not completed at Visit 13 or at ED)
- assessment of vital signs and body weight
- blood sampling for chemistry and hematology at Visit 13 or ED
- inquiries of AEs
- inquire about use of concomitant medications
- collection of blood sample to determine generation of anti-glargine antibodies at Visits 4, 8, 11, and Visit 13 (or ED)
- collection of serum samples for biomarker analyses during Visit 8 and Visit 13
- Health outcomes of the study will be measured as reflected in responses to ITSQ administered to the patients during Visit 13, (or ED), as indicated in the Study Schedule ([Attachment 1](#)).

In addition to the daily BG monitoring, patients will be required to complete the following, which are reviewed and/or transferred to eCRF during Visit 3 to Visit 13 or ED:

- 7-point SMBG profiles (described in Section [7.2.3](#)) on 2 separate days in the 1-week period prior to all investigator-site visits (or at ED) (preferably most recent readings).

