12.2.6. Primary Efficacy Outcome and Methodology

The primary efficacy outcome will be the change in HbA1c level from baseline to 24 weeks. The primary analysis will be a likelihood-based, MMRM approach, treating the data as missing at random (MAR) for the FAS population. The MMRM model will evaluate the change from baseline to each postbaseline visit in HbA1c level as the dependent variable with treatment (LY2963016, Lantus®), pre-study treatment (Lantus®-bolus, other basal-bolus, premixed insulin), and pre-study metformin or acarbose usage (metformin only, acarbose only, or neither), visit, and interaction between visit and treatment as fixed effects; the baseline value of HbA1c as a covariate; and a random effect for patient. The MMRM model will be carried out using the observed margins (OM) option in SAS. Using this option weights the levels of the independent or stratification variables according to the observed marginal distribution. This will provide least-squares means (LSMeans) for these outcomes that are more representative of the patient population recruited in this study.

The primary treatment comparison is to compare LY2963016 versus Lantus® at the NIM of +0.4%. If the upper limit of the 95% CI on the change from baseline to 24-week endpoint HbA1c for LY2963016 versus Lantus® is below +0.4%, then LY2963016 will be declared noninferior to Lantus®. The LSMean and standard error derived from the MMRM model for each treatment will be used to test noninferiority. Type III sums of squares will be used to make the treatment comparisons.

- If the +0.4% NIM is met, a key secondary treatment comparison is to compare Lantus® versus LY2963016 at the NIM of -0.4%. If the lower limit of the 95% CI on the change in HbA1c from baseline to the 24-week endpoint for LY2963016 versus Lantus® is above -0.4%, then Lantus® will be declared noninferior to LY2963016. The LSMeans and standard error derived from the MMRM model for each treatment will be used to test noninferiority. This gate-keeping procedure controls the family-wise Type 1 error rate at a 1-sided 0.025 level.
- If LY2963016 is declared noninferior to Lantus® in the primary treatment comparison, and Lantus® is declared noninferior to LY2963016 in this secondary treatment comparison, then LY2963016 will be considered to have equivalent efficacy as Lantus®.

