5.1.2.3. Blinded SSR Methodology

At the time of the blinded SSR, all available HbA_{1c} data in the database will be used. The HbA_{1c} value for subject i , and time t_j is denoted as y_{ij} , the total duration of the study is d , the subject random effect is, s_i , and the residual error is, ϵ_{ij} . The model for HbA_{1c} a Bayesian Integrated Two-Component Prediction (ITP) (Fu, 2010) and is written as,

$$y_{ij} = (\theta + s_i + \epsilon_{ij}) \frac{(1 - e^{-kt_j})}{(1 - e^{-kd})}$$

with the between subject error,

$$s_i \sim N(0, \sigma_b^2),$$

and within subject error,

$$\epsilon_{ij} \sim N(0, \sigma_w^2).$$

This model is Bayesian and requires specification of prior distributions for each parameter. For each parameter, non-informative priors have been chosen,

$$k \sim \text{Uniform}(0.001, 10),$$

$$\theta \sim N(-1, 1000),$$

$$\sigma_b^2 \sim \text{IG}(0.01, 0.01),$$

and

$$\sigma_w^2 \sim \text{IG}(0.01, 0.01).$$

This Bayesian model will be fit using Markov Chain Monte Carlo (MCMC) with the OpenBUGS package in R. The MCMC algorithm will use one chain, with initial values for the parameters drawn from their corresponding prior distributions. An appropriate burn-in period will be used of at least 10,000 iterations to ensure that the MCMC chain has reached convergence. After the burn-in period, 10,000 MCMC samples will be obtained for all parameters in the model, as well as all missing y data. Therefore each MCMC sample contains a complete predicted dataset,

where all unobserved y data are imputed. These 10,000 predicted datasets will be used to estimate the variability in HbA_{1c}. To ensure independence of the MCMC samples, the chains will be thinned by at least 10 to ensure that the 10,000 selected samples are not highly correlated. Diagnostics will be assessed to ensure convergence of the chain.

For each of the 10,000 MCMC samples, the primary analysis described in Section **Error! Reference source not found.** (containing all terms other than treatment assignment), will be performed using the complete dataset corresponding to each imputation step. For each of these k analyses, $k=1$ to 10,000, the total variability will be estimated, as $\hat{\sigma}_{T,k}$ by evaluating the residual error of the model. For each value of $\hat{\sigma}_{T,k}$, the estimated sample size will be computed using the sample size formula introduced in the previous section for a non-inferiority trial,

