5.2.7. Primary Efficacy Outcome and Methodology

The primary efficacy outcome will be the change in HbA1c level from baseline to 24 weeks. The primary analysis will be a likelihood-based, MMRM approach, treating the data as missing at random (MAR) for the FAS population. The MMRM model will evaluate the change from baseline to each postbaseline visit in HbA1c level as the dependent variable with treatment (LY2963016, Lantus®), pre-study treatment (Lantus®-bolus, other basal-bolus, premixed insulin), and pre-study metformin or acarbose usage (metformin only, acarbose only, or neither), visit, and interaction between visit and treatment as fixed effects; the baseline value of HbA1c as a covariate; and a random effect for patient. The MMRM model will be carried out using the observed margins (OM) option in SAS MIXED procedure. The standard least square means (LSMeans) have equal coefficients across classification effects; however, the OM option changes these coefficients to be proportional to the number of patients used to calculate the classification means. This will provide LSMean estimates that are more representative of the patient population recruited in this study.

The primary treatment comparison is to compare LY2963016 versus Lantus® at the NIM of +0.4%. If the upper limit of the 95% CI on the change from baseline to 24-week endpoint HbA1c for LY2963016 versus Lantus® is below +0.4%, then LY2963016 will be declared noninferior to Lantus®. The LSMean and standard error derived from the MMRM model for each treatment will be used to test noninferiority. Type III sums of squares will be used to make the treatment comparisons.

- If the +0.4% NIM is met, a key secondary treatment comparison will be conducted to show noninferiority of Lantus® to LY2963016. This will be done by comparing Lantus® versus LY2963016 at the NIM of -0.4%. If the lower limit of the 95% CI on the change in HbA1c from baseline to the 24-week endpoint for LY2963016 versus Lantus® is above -0.4%, then Lantus® will be declared noninferior to LY2963016. The LSMean and standard error derived from the MMRM model for each treatment will be used to test noninferiority. This gate-keeping procedure controls the family-wise Type 1 error rate at a 1-sided 0.025 level.

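### The primary MMRM fits one baseline-HbA1c slope to all four visits; a baseline-by-visit term would protect the Week 24 contrast, at almost no cost, if that slope changes during titration

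*SAP*

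**What the plan says.** The response is defined at every visit: "The MMRM model will evaluate the change from baseline to each postbaseline visit in HbA1c level as the dependent variable" (SAP 5.2.7). Protocol 7.2.2.4 schedules "collection of blood sample for HbA1c assessment to determine efficacy of treatment values for each patient at Visits 8, 11, 12, and Visit 13" or early discontinuation, which by the Study Schedule means Weeks 6, 12, 18 and 24.

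The covariate part of the model is "visit, and interaction between visit and treatment as fixed effects; the baseline value of HbA1c as a covariate; and a random effect for patient" (SAP 5.2.7). Protocol 12.2.6 agrees: "the baseline value of HbA1c as a covariate; and a random effect for patient". Neither lists a baseline-by-visit interaction. The per-protocol analysis reuses the model unchanged.

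On timing, protocol 7.2.1 expects that "most of the basal and bolus insulin dose adjustments should occur during the initial titration period (Week 0 through Week 6"), and adds that "titration could extend up to Week 12 for patients who need more intensification to achieve glycemic targets".

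The decision rests on Week 24 alone: "The primary treatment comparison is to compare LY2963016 versus Lantus® at the NIM of +0.4"%, judged by the upper 95% confidence limit.

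The subgroup MMRM in SAP 5.2.12 does include a subgroup-by-visit interaction, and entry HbA1c (split at 7% and at 8.5%) is among its subgroups. There the plan lets an entry-HbA1c effect vary by visit.

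**The concern.** Eligible patients may have any HbA1c up to 11%, and all are treated towards a target below 7%. Change therefore probably depends on baseline: patients who start high have further to fall. At Week 6 the main titration phase is only just ending, and HbA1c has not caught up with the latest dose changes. The regression of change on baseline could then be shallower at Week 6 than at Week 24.

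If so, a single slope is a compromise across visits and too shallow at Week 24. Two things follow. Some baseline variance that could have been removed stays in the Week 24 comparison and widens the interval tested against 0.4%. And the model implicitly predicts Week 24 for patients who left early with that same slope, which matters if the arms lose patients of different baseline HbA1c.

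**Working it through.** **1. The plan's own figure.** Inputs from SAP 5.1.1: margin 0.40, SD of change 1.05, true difference 0, two-sided 5%, 80% power, 15% dropout.

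- n per arm = 2(1.960 + 0.842)² × 1.05² / 0.40² = 108.2, so 109; power at 109 is 80.3%.
- 109 / 0.85 = 128.2, so 129 per arm, 258 in total.
- Half-width with no baseline adjustment: 1.96 × √(2 × 1.05² / 109) = 0.279.

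The stated figures reproduce. The SD of 1.05 is for change from baseline, and no reduction for baseline adjustment is mentioned.

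**2. Formula for the loss.** Let b24 be the true Week 24 slope, bc the fitted common slope, and s24² the Week 24 residual variance with visit-specific slopes.

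- s24² = 1.05² − b24² × Var(baseline)
- Variance with a common slope = s24² + (b24 − bc)² × Var(baseline)
- For a random-intercept model with complete data, bc is the simple mean of the four slopes. For an unstructured covariance Σ it is the weighted mean 1′Σ⁻¹b / 1′Σ⁻¹1.

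**3. Assumptions.** The documents give no visit-specific slopes, baseline SD or between-visit correlation. I assumed baseline SD 1.0 or 1.3; SD of change 1.05 at every visit, or 0.7/0.9/1.0/1.05; and correlation 0.6 exchangeable or 0.8 autoregressive.

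**4. One case in full.** Slopes −0.20/−0.35/−0.40/−0.45, baseline SD 1.0.

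- s24² = 1.1025 − 0.2025 = 0.900; half-width 1.96 × √(2 × 0.900/109) = 0.252; power 87.5%.
- Common slope as the simple mean: bc = −1.40/4 = −0.35. Extra variance (−0.10)² = 0.010, total 0.910; half-width 0.253, which is √(0.910/0.900) = 1.0055 times as wide; power 87.2%.
- Least favourable covariance in the grid: half-width 0.258, power 85.9%.

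**5. Grid.** Ratio of Week 24 half-widths, common slope to baseline-by-visit, unstructured covariance:

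| Assumed slopes, Weeks 6/12/18/24 | Ratio |
|---|---|
| −0.40 at all visits | 1.000 |
| −0.30/−0.40/−0.45/−0.45 | 1.001 to 1.021 |
| −0.20/−0.35/−0.40/−0.45 | 1.003 to 1.045 |
| −0.10/−0.30/−0.45/−0.50 | 1.005 to 1.092 |
| −0.10/−0.25/−0.40/−0.60 (extreme) | 1.005 to 1.116 |

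For the random-intercept model as worded, the model-based ratio runs from 1.00 to about 1.05. Across the grid the common-slope half-width is at most 0.264 and power at least 84%.

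**6. Simulation with dropout unrelated to baseline.** Random-intercept REML, 129 per arm, 15% dropout completely at random, baseline SD 1.1, SD of change 1.05 at all visits, 1,500 runs.

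- Slopes as in step 4: half-width 0.2489 against 0.2474 (0.6% wider), power 0.880 against 0.883.
- Extreme slopes: 0.2520 against 0.2458 (2.5% wider), power 0.908 against 0.928.
- Mean estimates were zero within simulation error for both models.

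**7. Simulation with dropout related to baseline in one arm only.** True difference 0, 129 per arm, about 15% dropout, odds ratio 2.7 per baseline SD in one arm, exchangeable correlation 0.6, 600 runs. Shift of the common-slope Week 24 contrast relative to the interaction model:

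- −0.30/−0.40/−0.45/−0.45: 0.014 to 0.017 points
- −0.20/−0.35/−0.40/−0.45: 0.023 to 0.032 points
- −0.10/−0.30/−0.45/−0.50: 0.04 to 0.05 points

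A separate simulation gave about 0.01 to 0.03. The interaction model stayed within 0.012 of zero. The sign depends on which arm loses its high-baseline patients: a too-shallow slope makes that arm look worse.

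**The case against.** The strongest objection is that the premise is assumed. No section reports a slope by visit. Most titration is meant to finish by Week 6, only some patients continue to Week 12, and with equal slopes the loss is zero. This stands, and it is why the point is conditional.

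A reader might infer from SAP 5.1.2.3 that the plan itself says dependence on baseline grows, because its re-estimation model, "a Bayesian Integrated Two-Component Prediction (ITP"), scales each patient's effect by (1 − e^(−kt))/(1 − e^(−kd)). It does not say so. That model has no baseline term and serves only the blinded variance estimate. Its prior for k runs from 0.001 to 10. If time is in weeks (the unit is not stated), k = 0.5 already puts the Week 6 factor at (1 − e^(−3))/(1 − e^(−12)) = 0.95 of its Week 24 value. The model permits growth after Week 6 without asserting it.

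A reader might also infer that the trial is underpowered or the contrast biased. Neither is supported. Steep Week 24 slopes, which create the loss, also make the existing covariate more useful, so power stays above plan. Randomization protects the contrast when dropout is unrelated to baseline. A wider interval is conservative in a noninferiority test.

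The supportive ANCOVA in SAP 5.2.7 fits its own endpoint slope, so the result does not rest on the common slope alone. It carries early values forward, however, so it is an imperfect check. What remains is dropout that depends on baseline differently by arm. The missing-at-random assumption permits it, and the trial is open-label, but nothing in the documents says to expect it.

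**Conclusion.** The concern holds as a minor refinement. The model imposes one baseline slope on four visits, and the titration schedule makes a changing slope plausible. Under moderate assumed slopes the Week 24 interval is about 0-4% wider than necessary; about 12% is reached only on extreme assumed paths. With dropout that depends on baseline in one arm, the estimate can shift by a few hundredths of a point against a margin of 0.4. These sizes rest on the assumed slopes, SDs, correlations and dropout mechanism listed above. Planned power is not threatened, and the noninferiority conclusion would not be invalid if the model were left as it is.

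**What to change.** Before database lock, add a baseline HbA1c-by-visit interaction to the primary MMRM in SAP 5.2.7 and protocol 12.2.6, and to the per-protocol MMRM that uses the same model. The cost is one model term, 3 degrees of freedom (four slopes in place of one) and a wording change; no new data are needed. If the slopes prove equal, essentially nothing is lost. The term should be prespecified, since adding it after results are seen would look data-driven. Extending it to the secondary and subgroup MMRMs is optional; nothing was calculated for those models.

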5.2.8. Secondary Efficacy Outcomes and Methodology

The continuous secondary efficacy outcomes include:

- actual and change in HbA1c from baseline to 6, 12, and 18 weeks or LOCF
- 7-point SMBG measurements and change from baseline to each visit (expressed as plasma-equivalent glucose values), as listed in the Study Schedule (see ABES Study Protocol Attachment 1)
 - premeal for each meal
 - postmeal for breakfast and lunch
 - bedtime
 - 3 am
- summaries of 7-point SMBG (actual and change from baseline)
 - daily mean BG level (average across all 7 time points)
 - daily mean premeal BG level (before breakfast, lunch, dinner)
 - daily mean postprandial BG level (breakfast, lunch and bedtime)
 - bedtime to 3 AM excursion
- inpatient variability as measured by the SD of the 7-point SMBG.

- actual and change from baseline total insulin, basal insulin, and mealtime insulin lispro doses in U/day and U/kg/day
- actual and change from baseline in weight and BMI
- patient-reported outcomes as reflected in responses to ITSQ.

The analysis of the continuous secondary efficacy variables will be performed using the same MMRM model with treatment (LY2963016, Lantus®), pre-study treatment (Lantus®-bolus, other basal-bolus, premixed insulin), and pre-study metformin or acarbose usage (metformin only, acarbose only, or neither), visit, and interaction between visit and treatment as fixed effects; the baseline value of the response variable and the baseline HbA1c level as covariates; and a random effect for patient, with the FAS population.

The proportions of subjects achieving HbA1c target values (HbA1c <7.0% and ≤6.5%) at any point during the study (Weeks 6, 12, 18, 24, and 24-week endpoint [LOCF]) will be analyzed using Fisher's Exact test or Pearson's Chi-square test.

A listing of 7-point SMBG and 4-point SMBG will be presented for all the randomized subjects.

5.2.9. Pharmacokinetic/Pharmacodynamic Analyses

Not applicable.

5.2.10. Health Outcome/Quality of Life Analyses

The Insulin Treatment Satisfaction Questionnaire (ITSQ) will be completed at baseline (Visit 2), prior to randomization and at Week 24 (Visit 13 or ED).

The following will describe the analyses details for ITSQ.

5.2.10.1. Insulin Treatment Satisfaction Questionnaire

The ITSQ is a validated instrument containing 22 items that assesses treatment satisfaction completed at weeks 0 (visit 2), and 24 (visit 13) or early discontinuation for persons with diabetes who are taking insulin. Items are measured on a 7-point scale in which lower scores reflect better outcomes. In addition to an overall score, the items that make up the 5 domains of satisfaction are categorized as:

- Inconvenience of Regimen (IR - 5 items)
- Lifestyle Flexibility (LF - 3 items)
- Glycemic Control (GC - 3 items)
- Hypoglycemic Control (HC - 5 items)
- Insulin Delivery Device (DD - 6 items).

All individual patient domain scores and overall scores will be calculated as the sum of the individual item scores in the domain or overall. If an item score is missing for a patient and ≤20% of the items within the domain (or overall) are missing for that patient, then impute the missing item score as the mean of all other patients with a non-missing same item score.

Individual patient with more than 20% missing items in a domain (or overall), the domain (or overall) score will be set to missing.

The individual raw and transformed domain scores are then calculated as follows: first, calculate the raw domain score as the mean of the items in the domain for that patient. Then, use the following formula to transform the raw domain scores on a scale from 0-100 where higher scores indicate better treatment satisfaction:

$$\text{Transformed domain score} = 100 * [(7 - \text{raw mean domain score}) / 6]$$

The individual raw and transformed overall scores are then calculated as follows: first, calculate the raw overall score as the mean of the items for that patient. Then, use the following formula to transform the raw overall score on a scale from 0-100 where a higher score indicates better treatment satisfaction:

$$\text{Transformed overall score} = 100 * [(7 - \text{raw mean overall score}) / 6]$$

The change from baseline to Week 24 or end of study transformed domain and overall scores will be analyzed using the ANCOVA model for the FAS population. The ANCOVA model will include treatment (LY2963016, Lantus®), pre-study treatment (Lantus®-bolus, other basal-bolus, premixed insulin), and pre-study metformin or acarbose usage (metformin only, acarbose only, or neither) as fixed effects and the baseline value of HbA1c as a covariate.

The transformed domain and overall scores will be analyzed using the ANCOVA model for the FAS population. The ANCOVA model will have treatment (LY2963016, Lantus®), pre-study treatment (Lantus®-bolus, other basal-bolus, premixed insulin), and pre-study metformin or acarbose usage (metformin only, acarbose only, or neither) as fixed effects and the baseline value of HbA1c as a covariate.

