10.2. Health Outcome/Quality of Life Measures

Self-reported patient questionnaires will be used to compare the health outcomes for the 2 insulins. This will be reflected in responses to ITSQ administered at baseline (Visit 2) and 24 weeks (Visit 13) or ED if a patient received at least one dose of study insulin.

The ITSQ is a validated instrument containing 22 items that assesses treatment satisfaction for patients with diabetes on insulin (Anderson et al. 2004). Items are measured on a 7-point scale, where lower scores reflect better outcomes. In addition to an overall score, the items that make up the 5 domains of satisfaction are categorized as:

- Inconvenience of Regimen (5 items)

- Lifestyle Flexibility (3 items)
- Glycemic Control (3 items)
- Hypoglycemic Control (5 items)
- Satisfaction with the Insulin Delivery Device (6 items)

All individual patient-domain scores will be calculated as the sum of the items in the domain. If an item score is missing for a patient and less than 20% of the items within the domain are missing for that patient, then the mean of all other patients' scores for that item will be imputed for the item. Otherwise, the domain score will be missing for the patient.

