12.2.8. Health Outcome/Quality of Life Analyses

The ITSQ will be completed at baseline (Visit 2), prior to randomization and at Week 24 (Visit 13 or ED). Change from baseline to Week 24 or end of study will be analyzed using the ANCOVA model for the FAS population.

All individual patient-domain scores will be calculated as the sum of the items in the domain. If an item score is missing for a patient and less than 20% of the items within the domain are missing for that patient, then the mean of all other patients' scores with nonmissing value for that item will be imputed for the item. Otherwise, the domain scores will be missing for the patient.

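### One missing item in a 5-item ITSQ domain is scored under the SAP but dropped under the protocol, and both fill missing items from other patients' answers

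*SAP*

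**What the plan says.** The ITSQ has 22 items on a 7-point scale in five domains: Inconvenience of Regimen (5 items), Lifestyle Flexibility (3), Glycemic Control (3), Hypoglycemic Control (5) and the delivery device (6). Patients complete it at Visit 2, before randomization, and at Visit 13 or early discontinuation. Comparing the arms on it is a secondary objective (Protocol 6.2, SAP 4.2).

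**When a missing item is filled.** Protocol 10.2 imputes when "less than 20% of the items within the domain are missing for that patient", and then: "Otherwise, the domain score will be missing for the patient". Protocol 12.2.8 repeats the same strict limit. SAP 5.2.10.1 uses a different one: "If an item score is missing for a patient and ≤20% of the items within the domain (or overall) are missing for that patient", with the complement "Individual patient with more than 20% missing items in a domain (or overall), the domain (or overall) score will be set to missing". The protocol mentions an overall score but gives no missing-item rule for it; the SAP adds one.

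**What it is filled with.** The SAP instruction is "then impute the missing item score as the mean of all other patients with a non-missing same item score". Protocol 12.2.8 has the same approach ("then the mean of all other patients" who answered that item). Neither text names an arm or a visit.

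**How the score is formed.** The SAP takes the raw domain score as the mean of the items and transforms it as 100 × (7 − raw mean)/6.

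**How changes are handled.** Protocol 12.2.1 and SAP 5.2.1 allow analysis changes that do not touch a principal feature without an amendment, provided the change and its justification are described in the SAP and/or the clinical study report.

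**The concern.** The two limits differ only at exactly 20%, and that is where the simplest missing-data pattern falls in two of the five domains: one skipped item out of five. Two programmers, one working from the protocol and one from the SAP, would analyse different sets of patients in those domains. The SAP does not flag the change or explain it.

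The second issue is the filled-in value, on which the documents agree. An average over all other patients ignores what this patient said on the related items. At Week 24 it mixes both arms, so the filled item carries almost no information about treatment. The effect is to pull the arm difference towards zero.

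**Working it through.** **Step 1. Apply both limits to each domain.** Inputs are the item counts in Protocol 10.2 and SAP 5.2.10.1; 5 + 3 + 3 + 5 + 6 = 22, as stated. Share missing = items missing ÷ items in the domain.

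| Score | Items missing | Share | Protocol (<20%) | SAP (≤20%) |
|---|---|---|---|---|
| Inconvenience of Regimen | 1 of 5 | 20.0% | score missing | item filled |
| Hypoglycemic Control | 1 of 5 | 20.0% | score missing | item filled |
| Delivery device | 1 of 6 | 16.7% | item filled | item filled |
| Lifestyle Flexibility, Glycemic Control | 1 of 3 | 33.3% | score missing | score missing |
| Any domain | 2 or more | 33.3% or more | score missing | score missing |

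For the 22-item total, 4/22 = 18.2% and 5/22 = 22.7%, so no whole number of items falls at exactly 20%. The choice between < and ≤ cannot matter there.

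**Step 2. How many patients the conflict could touch.** The documents give no item-missing rate. Assume each item is missing independently with probability p, and use the 218 planned completers as the base. The probability of exactly one missing item out of five is 5p(1−p)⁴.

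- p = 0.5%: 2.45%, or 5.3 of 218 patients
- p = 1%: 4.80%, or 10.5
- p = 2%: 9.22%, or 20.1
- p = 5%: 20.36%, or 44.4

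These patients have a domain score under the SAP and none under the protocol.

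**Step 3. Dilution of the Week 24 arm difference.** With 1:1 allocation (Protocol 9.3), an item filled from both arms has an expected arm difference of about zero. If the items contribute equally, a patient with one of five items filled carries 4/5 of the true domain difference. So dilution ≈ (share of scored patients with one item filled) × 1/5.

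- 5% of patients: 0.05 × 0.2 = 1%
- 20% of patients: 0.20 × 0.2 = 4%

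Under the independence model of Step 2, the share among scored patients is 5p(1−p)⁴ ÷ [(1−p)⁵ + 5p(1−p)⁴]. One fifth of it is 0.49%, 0.96%, 1.85% and 4.17% for the four values of p.

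The baseline form is completed before randomization, so pooling the arms there cannot dilute a treatment effect.

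**Step 4. What the choice of filled value can do to one patient.** Suppose four answers of 6, one item missing, and a mean of 3 among the other patients (an assumed case).

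- Filled from others: (4 × 6 + 3)/5 = 5.4, so 100 × (7 − 5.4)/6 = 26.7
- Own answers: mean 6, so 100 × (7 − 6)/6 = 16.7

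The two methods differ by 10 points on the 0–100 scale for this patient.

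**Step 5. The overall score.** A patient who skips a whole 3-item domain misses 3/22 = 13.6%. Under the SAP that domain score is missing, but an overall score is still formed, with three of its items supplied by other patients. Skipping a whole 5-item domain is 22.7%, above the limit, so the overall score is already missing there.

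**The case against.** The case on the other side is substantial, and much of it stands.

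- **The conflict is narrow.** It needs exactly one missing item, in one of two domains. This is correct.
- **An unexplained SAP change is not yet a breach.** The justification may still appear in the study report. This is also correct, but until then the two documents give opposite instructions.
- **The pooled item mean is not a discrepancy.** Both documents use it, and preferring the patient's own mean is a choice of method. True. The instrument's scoring instructions might require an item-mean rule; neither document says so, and even that could not explain two different limits.
- **The 10-point gap in Step 4 is not an error.** A reader might infer that the SAP scores such a patient wrongly. That would treat the patient's own mean as the truth. If the missing answer were really 3, 26.7 would be the exact score and the own-answer method would be 10 points off.
- **Silence about the visit is not a plan to pool visits.** The text can be read as meaning the same visit. It needs a clarification, no more.
- **The overall-score case is not a contradiction.** Missing 13.6% is inside the SAP's own overall limit, and 19 of the 22 items are still the patient's own.

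**Conclusion.** The threshold conflict is exact and can be read off the texts. It decides whether a patient with one skipped item is scored in Inconvenience of Regimen and Hypoglycemic Control, and it affects no other domain.

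The shared method of filling items from other patients is a small weakness. It dilutes the Week 24 arm difference in a 5-item domain by about 1% if 5% of patients miss one of the five items, and by 4% if 20% do. These figures rest on assumed missing rates, 1:1 arms and roughly equal item effects.

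A reader might infer that pooling the arms helps the biosimilar claim in an open-label trial. The documents do not support that. The ITSQ objective is only to compare the arms and has no margin; non-inferiority and equivalence are decided on HbA1c alone (SAP 5.2.7), which this rule does not touch. The point is a low-priority improvement to a named secondary outcome.

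**What to change.** In SAP 5.2.10.1:

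1. State one limit, ≤20%, note that it differs from the strict limit in Protocol 10.2 and 12.2.8, and give the reason.
2. Score each domain as the mean of the patient's own answered items when ≤20% are missing, and otherwise set it to missing. The SAP raw score is already a mean, so the transformation is unchanged.
3. For the overall score, when ≤20% of the 22 items are missing, fill each missing item with the mean of the patient's own answered items in that domain. This includes a 3-item domain with one item missing, whose own domain score stays missing. Set the overall score to missing if any domain has no answered item.
4. If the item mean over other patients is kept because the instrument's scoring instructions require it, say so and specify that the mean is taken at the same visit.

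The cost is a short edit to one SAP subsection before database lock; under Protocol 12.2.1 it can be made in the SAP without a protocol amendment if it is not treated as a principal feature. The downside is that overall scores are lost for the few patients who skip a whole 3-item domain but are otherwise within the 20% limit.
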